## SYNOPSIS

TITLE	Evaluating the Use of Preemptive Pharmacogenomic Testing to Personalize Supportive Oncology
STUDY POPULATION	Adult cancer patients $\geq 18$ y/o presenting with moderate to high pain ( $\geq 4/10$ ) and/or depression ( $\geq 3/10$ or patients diagnosed with depression with a clinical need to adjust depression medications) on the Edmonton Symptom Assessment Scale (ESAS) during the initial consultation or a follow-up visit that occurs more than 1 year since the last visit in the palliative medicine clinic, able and willing to sign informed consent, and able to provide a buccal sample for pharmacogenetic testing.
SUMMARY OF STUDY RATIONALE	Over 90% of cancer patients experience cancer- or treatment-related symptoms, including pain and depression. At least 50% have uncontrolled symptoms throughout their lifetime. This significantly impacts patients' quality of life, response to therapy, and potentially survival. Many medications used to treat these symptoms are plagued with a system of trial and error, with prolonged time to symptom control or improvement. Objective tools are needed to improve drug selection and reduce symptom burden. Pharmacogenetics (PGx) allows for personalized medical decisions based on patient-specific genetics and provides a unique opportunity to reduce arbitrary drug selection and improve personalized prescribing, especially for pain and depression medications. By studying the application of a PGx test to alter drug prescribing patterns and improve treatment outcomes in supportive oncology, these results will provide critical information to understand the feasibility and utility of performing preemptive, real-time PGx testing. We believe this study will help shift supportive care prescribing paradigms from a trial-and-error approach to a personalized, genomics-driven method. Ultimately, using PGx to optimize medication selection and control cancer-related symptoms may improve quality of life throughout the cancer care continuum, potentially extending overall survival.
STUDY DESIGN	This is a prospective clinical trial of adult cancer patients presenting with pain and depression, newly referred to the Department of Supportive Oncology's palliative medicine clinic (or previously established patients without a visit in the past year) and receiving PGx testing for genes related to supportive care prior to their Baseline study visit. Patients will be screened and identified for eligibility after their initial consultation in palliative medicine. If meeting the ESAS score cutoffs for pain and depression and meeting all other eligibility criteria, patients will be approached for consent and undergo buccal swabs collection after informed consent is obtained. Genotyping results will be returned within approximately 4-5 business days. A PGx specialist will provide detailed clinical interpretations to the referring provider and upload a copy of the test results into the subject's medical chart. A consultation note will also be placed in each subject's chart detailing the pharmacogenomics results. Supportive Oncology clinicians will be instructed to consult a pharmacist to evaluate PGx test results prior to prescribing supportive care therapies, especially pain and depression medications. The number of consults and recommendations will be documented, in addition to test results, demographic data, medical/medication history, ESAS symptom scores, PHQ9 depression scores, and side effects of supportive therapy. The

	
number of ambulatory clinic visits and hospitalizations will be used to estimate health care utilization and costs. Subjects will complete a short survey at the end of the study period regarding their knowledge about PGx, and whether access to PGx information improves satisfaction with care and communication.

OBJECTIVES	
Primary Objective:
 
 
• To estimate the proportions of subjects undergoing PGx testing who receive at least one drug/dose selection or modification based on their test results within any of the study visits where PGx results are available.
 
•
 
 
Secondary Objectives:
 
 
• To determine the impact of PGx on treatment outcomes by measuring pain scores using the Edmonton Symptom Assessment Scale (ESAS) (Appendix A) and depression scores using the Patient Health Questionnaire (PHQ) 9 (Appendix B) at study visits after the Baseline study visit. Symptom scores will also be compared between those receiving PGx testing and a matched control receiving clinical management alone.
 
• To describe subject perspectives (Appendix C) of PGx testing using a survey administered to subjects after/at the Final visit (or sooner if withdrawn).
 
•
 
 
Exploratory objectives:
 
 
• To determine the types & frequencies of actionable genotypes that result in drug/dose selection or modification(s) and those that do not result in drug/dose selection or modification(s).
 
• To describe the types of new medications prescribed (using medications of interest list; Appendix D) or medication/dose adjustments based on the PGx results.
 
• To determine the type & frequency of drug/gene interactions present at the Baseline and the Final study visit using CPIC guidelines and FDA’s pharmacogenomics table.
 
• Summarize PGx best practice advisory alerts among participants enrolled after the transition to Epic to describe the proportion of participants that had a BPA fire in the EMR, the number and type of BPAs per participant, and any actions taken from the BPA.
 

KEY INCLUSION CRITERIA	
 
• Adult cancer patients <math>\geq 18</math> years of age who have had either an initial visit in the Department of Supportive Oncology’s palliative medicine clinic or a re-establishment of care visit with the last visit being at least 1 year prior, able and willing to sign the informed consent and provide a buccal sample for PGx testing.
 
• Hematologic malignancy or any stage solid tumor malignancy. Presenting with pain score <math>\geq 4/10</math> and/or depression score <math>\geq 3/10</math> on ESAS (or patients diagnosed with depression with a clinical need to adjust depression medications)
 

STATISTICAL CONSIDERATIONS	
The evaluable population for the primary objective is defined as enrolled subjects with confirmed malignancy (per provider documentation) completing an on-study visit with PGx results available. We anticipate enrolling 80 eligible subjects, of which we estimate 65 will be evaluable.

	With this sample size, the width of the 95% Clopper-Pearson confidence interval will be $\leq 25\%$ , regardless of the observed DDSM rate.
NUMBER OF SUBJECTS	80, to achieve 65 evaluable subjects

# 1. BACKGROUND AND RATIONALE

## 1.1 Background

Early palliative care after diagnosis with incurable cancer improves quality of life (QOL) and may prolong overall survival [1-7]. However, there is large inter-individual variability in response to supportive care medications, such as those for pain and depression [6,8]. Pain affects more than 75% of cancer patients with advanced disease. Less than one-third of all patients achieve pain improvement with conventional strategies within one month of presentation [9]. Depression affects about one-third of cancer patients and has been linked to poorer prognosis and survival [10-13]. Pain, depression, and fatigue often coexist as a symptom cluster in cancer patients [14,15]. The combined effects of pain and depression is a significant public health crisis, particularly in the era of the opioid epidemic. Patients with moderate to severe depression are more than twice as likely to misuse opioids for non-pain symptoms compared to non-depressed patients [16]. Improper opioid prescribing has prompted the Center for Disease Control and Prevention (CDC) to issue guidelines for improving prescribing to mitigate abuse and addiction concerns [17]. Suboptimal management of cancer-related symptoms like pain and depression compromises potential cancer therapy benefits, disrupts clinic workflow, increases emergency room visits, and impacts patient satisfaction [18].

Pharmacogenomics (PGx) – the impact of genetic variation on drug response – is well documented [19] and can significantly impact response to supportive therapy, especially pain and depression medications [18,20]. Data suggests >90% of individuals carry a PGx variant contributing to drug response [21]. As this data grows along with more affordable analytic technology, it will soon be standard of care to perform routine PGx testing prior to treatment. The truest value of this data can only be fully realized when it is implemented preemptively into the routine workflow and embedded within care pathways, as discussed in previous reviews [21,22]. The Clinical Pharmacogenetics Implementation Consortium (CPIC) has thus far published approximately 45 drug-specific, peer-reviewed guidelines on how to best apply PGx to guide therapy (at least a dozen of which are related to supportive care medications) [23]; however, there is also an emerging level of relevant genes not currently covered by these guidelines. Effective integration of PGx-guided treatment pathways can help personalize medication selection in supportive oncology [18,20] and help determine the magnitude of drug-drug and drug-drug-gene interactions [24]. Several genes have been implicated with response to supportive care medications (Table 1).

Table 1. Summary of potential drug-gene interactions

Gene	Polymorphism(s)/variant(s)	Supportive care medications potentially affected
CYP3A4	*1B, *22	Oxycodone, hydrocodone, fentanyl, methadone
CYP3A5	*3, *6, *7	Oxycodone, hydrocodone, fentanyl, methadone
CYP2D6	*2, *3, *4, *5, *6, *9, *10, *17, *29, *41, duplications/copy number variations	Codeine, tramadol, oxycodone, hydrocodone, ondansetron, amitriptyline, imipramine, clomipramine, desipramine, doxepin, fluvoxamine, nortriptyline, fluoxetine, paroxetine, duloxetine, atomoxetine, amphetamines,
CYP2C9	*2, *3, *6, *8, *11	Diclofenac, ibuprofen, meloxicam, celecoxib, phenytoin
CYP2C19	*2, *3, *17	Esomeprazole, lansoprazole, omeprazole, pantoprazole, amitriptyline, citalopram, clomipramine, doxepin, escitalopram, imipramine, sertraline
CYP2B6	*4, *5, *6, *18	Methadone, bupropion, ketamine
COMT	Val158Met	All opioids
OPRM1	118A>G	All opioids
SLC6A4	Short or long allele	Selective Serotonin Reuptake Inhibitors
HTR2A	rs7997012	Citalopram

Opioid PGx: CYP2D6 activates codeine, tramadol, oxycodone, and hydrocodone to stronger opioids: morphine, o-desmethyltramadol, oxymorphone, and hydromorphone, respectively. CYP2D6 polymorphisms can significantly alter opioid pharmacology [25]. For example, codeine-related deaths reported in ultra-rapid metabolizers (UMs) resulted in a black-box warning recommending against its use [26-32]. Alternatively, poor metabolizers (PMs) may have ineffective analgesia due to impaired activation to morphine. Similar mechanisms are noted with tramadol, oxycodone, and hydrocodone [33-37]. CPIC recommends CYP2D6 UMs and PMs avoid codeine, tramadol, oxycodone and hydrocodone due to increased toxicity or lack of analgesia, respectively [38]. A base-pair substitution in the gene coding the mu-opioid receptor, OPRM1, can result in 60%–100% more morphine required for equal analgesia [39-41]. Analgesia can also be enhanced by presence of catecholamines, which are metabolized by the enzyme COMT. A base-pair substitution in COMT reduces enzyme activity by 3-4-fold, increases catecholamine exposure, increases opioid sensitivity, and lowers morphine equivalents required for analgesia, whereas those with higher activity may require at least doubling of the dose [39,42,43].

Antidepressant PGx: CYP2C19 metabolizes and inactivates citalopram, escitalopram, and sertraline. CYP2C19 PMs have increased toxicity risk with these medications, including QT prolongation [44,45]. Alternatively, UMs have lower plasma concentrations and increased risk of not responding [46]. CPIC recommends a 50% dose reduction in citalopram, escitalopram, and sertraline for CYP2C19 PMs and avoiding the drugs in UMs [47]. Paroxetine is primarily metabolized by CYP2D6; thus, PMs are at increased risk of adverse effects, particularly gastrointestinal [48,49], while UMs are at risk of poor drug response [50]. CPIC recommends avoiding paroxetine in CYP2D6 UMs and PMs [47]. Fluoxetine is metabolized by CYP2D6 and CYP2C19, thus similar mechanisms can influence drug response. Vortioxetine is primarily metabolized by CYP2D6 and the FDA label recommends a maximum dose of 10 mg/day in PMs [51]. Polymorphisms in the serotonin transporter gene, SLC6A4, and/or serotonin receptor gene, HTR2A, may result in reduced response to selective serotonin reuptake inhibitors. Randomized trials have

shown better clinical response with PGx-guided antidepressant selection [52-54] and tools have been developed to assist with PGx-based antidepressant prescribing [55,56].

PGx tests are now commercially available; however, due to their novelty, healthcare payors are reluctant to reimburse preemptive PGx screening and mandate further proof-of-concept and efficacy trials before coverage. Nonetheless, preemptive PGx testing increases the value proposition and prior studies suggest improved medication adherence and cost savings with PGx [57,58]. Further, many of the genes discussed earlier can affect non-oncology or non-supportive oncology medications that may be prescribed by other providers within the same health system (e.g., clopidogrel and CYP2C19). PGx results may be informative for management of other medications. Despite widespread availability of PGx tests and declining diagnostic costs, there is little data on the practicality of using PGx to improve supportive cancer care.

The Edmonton Symptom Assessment Scale (ESAS) (Appendix A) is a validated 10-item questionnaire assessing self-reported perceptions of pain, fatigue/energy, nausea, depression, anxiety, drowsiness, appetite, wellbeing, and shortness of breath. Each item is ranked from 0 to 10, with 10 representing the worst symptom. ESAS is routinely performed during all palliative medicine clinic visits. ESAS can be used to identify cancer patients presenting to palliative medicine with uncontrolled symptoms and can also be used to track symptom improvement or progression over time.

In a prior analysis we identified 46% of cancer patients at Levine Cancer Institute were prescribed a supportive care medication within 90 days of intake to the cancer hospital, mainly for pain (69%) and/or nausea (46%). Of these, 86% received at least one supportive care medication with PGx evidence and 84% received a CYP2D6-metabolized drug. Based on reported CYP2D6 allele frequencies conferring altered metabolism, 650 (20%) were expected to have altered drug response, suggesting preemptive PGx testing may have broad applicability in this population. PGx testing in this high-risk population may improve medication management and symptom control.

## 1.2 Study Rationale and Study Design

Over 90% of cancer patients experience cancer- or treatment-related symptoms, and at least 50% have uncontrolled symptoms throughout their lifetime. This significantly impacts patients' QOL, response to therapy, and potentially survival. Thus, guidelines recommend early palliative intervention for all cancer patients with advanced disease; however, many medications used to treat these symptoms are plagued with a system of trial and error, with prolonged time to symptom control or improvement.

Objective tools are needed to improve drug selection and reduce symptom burden. PGx allows for personalized medical decisions based on patient-specific genetics and provides a unique opportunity to reduce arbitrary drug selection and improve personalized prescribing. By studying the application of a PGx test to alter drug prescribing patterns for pain and depression and improve treatment outcomes in supportive cancer care, these results will provide critical information to understand the feasibility and utility of

performing preemptive, real-time PGx testing in a busy, outpatient clinic. This study will help shift supportive care prescribing paradigms from a trial-and-error approach to a personalized, genomics-driven method. Ultimately, using PGx to optimize medication selection and control cancer-related symptoms may improve QOL, as measured by aggregate ESAS scores, throughout the cancer care continuum, potentially extending overall survival.

We propose a prospective clinical trial of adult cancer patients at Levine Cancer Institute presenting to the Department of Supportive Oncology's palliative medicine clinic with moderate to high pain and depression (screened using ESAS at initial palliative medicine visit). Genotyping results will be returned within five business days. A PGx specialist will provide detailed clinical interpretations to the palliative medicine clinic and upload a copy of the results as well as a clinic note into the subject's medical chart. Each subject will also be counseled on their test results. A note will be placed in each subject's chart alerting the provider that the subject is on study and should be referred for pharmacy consultation to evaluate PGx test results prior to prescribing supportive therapy during the study period. The number of pharmacy consults for subjects undergoing PGx testing, type of medication recommendations, actionable genotypes, and rate of acceptance by the provider will be documented. Other data elements to be collected include all PGx test results, demographic data, medical/medication history, ESAS (Edmonton Symptom Assessment System) symptom scores, and PHQ9 (Patient Health Questionnaire) scores. The number and duration of emergency department visits and hospitalizations will be used to estimate health care utilization and costs. Subjects will complete a short survey at the end of the study period (from enrollment [day of the buccal swab] to the Final visit) regarding their knowledge about PGx, and whether access to PGx information improves satisfaction with care and communication.

## **2. STUDY OBJECTIVES AND ENDPOINTS**

### **2.1 Objectives**

#### **2.1.1 Primary Objective**

- Estimate the proportions of subjects undergoing PGx testing who receive at least one drug/dose selection or modification based on their test results within any of the study visits where PGx results are available.

#### **2.1.2 Secondary Objectives**

- Determine the impact of PGx on treatment outcomes by measuring pain scores using the Edmonton Symptom Assessment Scale (ESAS) ([Appendix A](#)) and depression scores using the Patient Health Questionnaire (PHQ) 9 ([Appendix B](#)) at study visits after the Baseline study visit. Symptom scores will also be compared between those receiving PGx testing and a matched control receiving clinical management alone.
- Describe subject perspectives ([Appendix C](#)) of PGx testing using a survey administered to subjects after/at the Final visit (or sooner if withdrawn).

### 2.1.3 Exploratory Objectives

- Determine the types & frequencies of actionable genotypes that result in drug/dose selection or modification(s) and those that do not result in drug/dose selection or modification(s).
- Describe the types of new medications prescribed (using medications of interest list; [Appendix D](#)) or medication/dose adjustments based on the PGx results.
- Determine the type & frequency of drug/gene interactions present at the Baseline and the Final study visit using CPIC guidelines and FDA's pharmacogenomics table.
- Summarize PGx best practice advisory alerts among participants enrolled after the transition to Epic to describe the proportion of participants that had a BPA fire in the EMR, the number and type of BPAs per participant, and any actions taken from the BPA.

## 2.2 Endpoints

### 2.2.1 Primary Endpoint

A binary variable will be recorded for each subject undergoing PGx testing to indicate whether or not the subject received at least one drug/dose selection or modification based on their test results at any study visit where PGx results were available.

### 2.2.2 Secondary Endpoints

- A count variable will be recorded for each subject undergoing PGx testing indicating the total number of drug/dose selections or modifications received across all study visits where PGx results were available.
- Pain scores assessed by the ESAS and depression scores using PHQ9 will be recorded for each subject at the Baseline and all the visits.
- Health care resource utilization (HCRU) and costs will be estimated based on the number of inpatient, emergency department, outpatient, and pharmacy encounters, among others, occurring one year prior to and during the study period.
- Discrete variables will be recorded to indicate subject survey responses.

### 2.2.3 Exploratory Endpoints

- Binary variables will be recorded for each subject, indicating the presence or absence of an actionable genotype for each of the tested genotypes.
- Discrete variables will be recorded for each subject indicating the new medications prescribed or medication/dose adjustments made using the PGx results.
- Discrete variables will be recorded for each subject indicating the drug/gene interactions present at the Baseline and at the Final study visit. A count variable indicating the number of interactions will also be recorded.
- PGx best practice advisory (BPA) alerts: BPA alerts are fired within Epic when there is presence of a drug-gene interaction at the time of medication order entry. The following will be determined for study participants enrolled after the transition to Epic: a binary variable indicating the presence of a BPA in their EMR and a count variable indicating the total number of BPAs in their EMR.

### 3. SUBJECT SELECTION

#### 3.1 Subject Identification and Recruitment

Accrual is expected to be 80 eligible subjects. All patients will complete ESAS during a regularly scheduled visit to the Department of Supportive Oncology's palliative medicine clinic (Palliative medicine clinic). Potential candidates will be identified by reviewing the EMR to identify patients with ESAS pain  $\geq 4/10$  and/or depression  $\geq 3/10$  (or diagnosed with depression with a clinical need to adjust depression medications).

It is expected that 80 eligible subjects will be required to enroll 65 evaluable subjects. In the event that more subjects are required to achieve 65 evaluable subjects, subject enrollment will continue until 65 evaluable subjects have been enrolled.

Target accrual period of this study will be approximately 30 months.

#### 3.2 Inclusion Criteria

**Subjects must meet all of the following criteria:**

1. Written informed consent and HIPAA authorization for release of personal health information
2. Completion of ESAS at initial palliative medicine clinic visit, presenting with moderate to high pain ( $\geq 4/10$ ) and/or depression ( $\geq 3/10$ ) or diagnosed with depression with a clinical need to adjust depression medications identified by the provider.
3. New patients  $\geq 18$  years of age who have had either an initial visit in the Department of Supportive Oncology's palliative medicine clinic or a re-establishment of care visit with the last visit being at least 1 year prior to the date of consent, with hematologic malignancy or any stage solid tumor malignancy according to the provider. Patients without confirmation of malignancy at the time of enrollment can be enrolled based on radiographic evidence suggesting the likelihood of malignancy per investigator discretion.
4. Agree to at least one additional palliative medicine clinic visit per protocol.
5. Able to provide a buccal sample for PGx testing

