## **5. STUDY PLAN**

The study design is a prospective interventional clinical trial designed to investigate the application of PGx testing to personalize cancer symptom management, particularly pain and depression.

Potential candidates will be presented with consent; screening data for these patients, including ESAS symptom scores, will be captured and used for analysis ([Section 11.4.5](#)). A full waiver of consent and HIPAA for data collection will be requested for the control cohort, which includes patients (with pain  $\geq 4/10$  and/or depression  $\geq 3/10$  who have not been presented with consent and who were presented with consent but decline participation in the study (i.e., do not consent). Study subjects who consent and subsequently screen fail for any reason will also be included in the control cohort. Patients who agree will undergo the informed consent process, and subjects who consent will be screened for eligibility. Those meeting eligibility criteria will be enrolled and undergo buccal swab collection. **Enrollment day** will be considered at the **buccal swabs collection day**. If the collected buccal swabs do not contain enough viable DNA for PGx testing, subjects may be asked to provide additional swabs. No less than 2 weeks and no more than 8 weeks should pass between the first ESAS completion and the date of the **Baseline study visit**. **The Baseline study visit** may be completed during a clinic visit (in person or virtually) or over the phone. It is estimated that PGx results will be available within five business days of swab receipt by the laboratory, and a detailed report will be sent to the clinic. A copy of the test results in PDF (Portable Document Format) format and PGx consultation note will be uploaded to the subject's medical chart. Apart from the availability and use of PGx test results to guide pharmacotherapy, subjects will receive standard of care treatment and undergo ESAS screening during the palliative medicine visits. PHQ9 will be collected by the research team electronically, during the study visit by paper, or by phone. Data, including symptom scores and medications, at each visit, will be captured until the **Final study visit**. Subjects will be asked to complete a short survey within 30 days after the Final study visit to assess their perspectives on PGx testing and the care they received (administered preferably electronically, alternatively via paper during the Final visit at a clinic or over the phone).

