### 11.4.5 Secondary Analysis

Total counts and descriptive statistics of the number of drug/dose selection/modifications made due to subject PGx test results at all visits where PGx results are available will be summarized.

A single-arm analysis for the PGx cohort will be performed: Descriptive statistics of ESAS pain scores and PHQ-9 depression scores will be calculated and summarized at study visits. Repeated-measures linear mixed models will be estimated for pain and depression, separately, adjusted for baseline clinicodemographic characteristics and include a main effect for time and a random effect for subject.

The following analysis will be performed for both the PGx and control cohorts:

A matched analysis for ESAS pain and depression scores will be carried out, comparing the study cohort to a matched cohort of unique patients receiving clinical management alone during the same time period the trial is enrolling. Standard-of-care patients with ESAS pain  $\geq 4$  and/or depression scores  $\geq 3$  at their first visit to the palliative medicine clinic or a re-establishment of care visit with the last visit being at least 1 year prior—these visits occurring within the same time period the trial is enrolling—will be identified and considered in the matched analysis.

Enrolled subjects will be matched to a similar case in cohort by:

- ESAS pain and depression symptom scores at first visit to palliative medicine clinic (i.e., study screening for study cohort)
- Age
- Sex
- Race
- Clinic visit schedule.

Between-group comparisons of those study subjects and control patients will be performed estimating repeated-measures linear mixed models for pain and depression, separately, to estimate the effect of PGx testing (i.e., treatment effect) on symptom scores adjusted for baseline clinicodemographic characteristics, a main effect for treatment, for time, an effect for treatment by time interaction, and a random effect for subject.

Additionally, the average post-baseline symptom score will be calculated for each individual (separately for pain and depression). The distributions of the average post-baseline symptom scores will be compared between the cohorts using analysis of variance techniques with adjustments for clinicodemographic characteristics.

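### PGx subjects can enter on a depression diagnosis with no minimum ESAS score, but matched controls must meet an ESAS cutoff, so PGx subjects below both cutoffs have no equal-score control in the section 11.4.5 pool

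*Combined protocol and SAP*

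**What the plan says.** Inclusion criterion 2 in section 3.2 gives the PGx cohort three routes in: ESAS pain of at least 4, ESAS depression of at least 3, "or diagnosed with depression with a clinical need to adjust depression medications identified by the provider". Section 3.1 and the synopsis repeat the third route, so it is not a slip.

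Controls are defined more narrowly. Section 11.4.5 describes them as "Standard-of-care patients with ESAS pain $\geq 4$ and/or depression scores $\geq 3$ at their first visit to the palliative medicine clinic" (or at a re-establishment visit), and it is these patients who "will be identified and considered in the matched analysis". Section 5 applies the same cutoffs to patients "who have not been presented with consent and who were presented with consent but decline participation in the study". It then adds everyone who consents and later fails screening, whatever the reason, and states no cutoff for them. Neither section gives controls the diagnosis route.

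The first matching variable in section 11.4.5 is "ESAS pain and depression symptom scores at first visit to palliative medicine clinic". The others are age, sex, race and visit schedule; depression diagnosis is not among them. Matching is to a comparable patient, with no algorithm, ratio, caliper or rule for subjects who cannot be matched. The between-group models adjust for clinicodemographic characteristics, and first-visit ESAS scores are not named among these. Section 11.3 keeps diagnosis-route subjects in the symptom-score analyses.

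**The concern.** The two cohorts have different entry rules, and they differ on the variable used to match them. A PGx subject below both ESAS cutoffs is eligible, but section 11.4.5 admits no control with those scores. The analyst must then choose, after the data are in, between a control with a worse first-visit score and no match at all. The first choice builds a starting difference into the comparison. The second narrows the population that the estimate describes.

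This is the plan's only between-group estimate of the effect of PGx testing on symptoms, and it serves a stated secondary objective (section 2.1.2).

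**Working it through.** The plan gives no power or precision figure for the matched comparison, so there is none to reproduce. Its only sizing figure, the confidence-interval width for the primary proportion in section 11.2, plays no part here.

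**Inputs from the documents.** ESAS items are integers from 0 to 10 (Appendix A); the cutoffs are pain ≥4 and depression ≥3; 65 evaluable subjects are expected (section 11.2).

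**Assumptions, none given in the documents.** Share of PGx subjects below both cutoffs 5%, 10% or 20%; correlation between first-visit and later scores 0.5; SD 2 to 2.5; 65 per cohort; the 12 score pairs below equally likely; each subject matched to the nearest allowed score; no adjustment for first-visit score.

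**Step 1: overlap.** There are 11 × 11 = 121 (pain, depression) pairs. Pairs below both cutoffs: 4 × 3 = 12. Pairs allowed for controls by section 11.4.5: 121 − 12 = 109. Pairs in both sets: 0.

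**Step 2: distance to the nearest allowed control.** Gap = min(4 − pain, 3 − depression), with the other score equal. D means the gap falls on depression, P on pain, T a tie.

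| | Depression 0 | Depression 1 | Depression 2 |
|---|---|---|---|
| Pain 0 | 3 D | 2 D | 1 D |
| Pain 1 | 3 T | 2 D | 1 D |
| Pain 2 | 2 P | 2 T | 1 D |
| Pain 3 | 1 P | 1 P | 1 T |

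The range is 1 to 3 and the control is always the higher. The total is 20, a mean of 20/12 = 1.67.

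**Step 3: split by outcome.** Pain and depression are modelled separately, so the gap must be divided. Of the 20 points, 10 are D, 4 are P and 6 are T. Depression carries 10 to 16 points (mean gap 10/12 = 0.83 to 16/12 = 1.33). Pain carries 4 to 10 points (0.33 to 0.83).

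**Step 4: bias in post-baseline level.** Bias = share × mean gap × correlation. At 20%, depression is 0.20 × 0.83 × 0.5 = 0.08 to 0.20 × 1.33 × 0.5 = 0.13. Pain is 0.20 × 0.33 × 0.5 = 0.03 to 0.20 × 0.83 × 0.5 = 0.08.

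**Step 5: relative to the standard error.** A simple unpaired SE is SD × √(2/65), which is 0.35 at SD 2 and 0.44 at SD 2.5.

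| Share | Depression, points | Depression, SE | Pain, points | Pain, SE |
|---|---|---|---|---|
| 5% | 0.02–0.03 | 0.05–0.10 | 0.01–0.02 | 0.02–0.06 |
| 10% | 0.04–0.07 | 0.10–0.19 | 0.02–0.04 | 0.04–0.12 |
| 20% | 0.08–0.13 | 0.19–0.38 | 0.03–0.08 | 0.08–0.24 |

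Bias scales with the correlation: at 0.7 every entry is multiplied by 1.4.

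**Step 6: cost of restricting the analysis.** With 3, 6 or 13 of 65 subjects set aside, 62, 59 or 52 remain. The SE rises by √(65/62) = 1.02, √(65/59) = 1.05 or √(65/52) = 1.12.

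**The case against.** Several stronger readings are tempting, and the documents do not support them.

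- **These subjects have no possible control.** This holds for equal scores within the section 11.4.5 pool. Section 5, however, puts screen failures into the control cohort with no cutoff stated, and a few could score below both cutoffs. The group is probably small, and section 11.4.5 may filter it out. That makes the two sections inconsistent; it does not prove the pool empty.
- **The plan drops these subjects.** No such rule exists. Matching asks only for a comparable patient, and a control 1 point away may qualify. Going unmatched is one possible outcome.
- **The bias favours PGx.** Unadjusted post-baseline levels would lean that way, because the matched controls start higher. But if the first visit enters the model, the controls' excess shrinks over follow-up, and the treatment-by-time term leans the other way. Diagnosed patients whose usual depression score is higher than their first-visit score would also offset the gap. Adjustment might absorb part of it.
- **The bias reaches 0.17 points.** Charging the whole mean gap to one outcome gives 0.20 × 1.67 × 0.5 = 0.17. Step 3 shows that neither outcome can carry all of it under these assumptions.

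It is also fair to say that only subjects below both cutoffs matter: a diagnosis-route subject with pain of 4 or more has controls available. The comparison is secondary and non-randomised. What stands is the mismatch itself and the absence of any rule for handling it.

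**Conclusion.** The mismatch in entry rules is certain from the text: no score pair below both cutoffs is allowed in the section 11.4.5 control pool, and the nearest allowed pair is 1 to 3 points higher on one score. Depending on how similarity is judged, the affected subjects may be given controls with worse first-visit scores or may go unmatched.

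The effect on the estimate is modest and uncertain. At an assumed 20% share it is roughly 0.1 to 0.4 SE, and it is small at 5–10%. These figures rest on the assumptions listed in the working. Two of these could move them in opposite directions: adjusting for first-visit score would reduce the bias, and accepting a control further away than the nearest, to satisfy age, sex, race or visit schedule, would increase it.

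Only the secondary matched ESAS comparison, and any matched-control cost data built on the same pairs, are affected. The primary proportion, the modification counts and the single-arm models are not. The change is worth making because it is cheap and removes a choice otherwise made after the data are seen.

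**What to change.** In section 11.4.5:

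1. Restrict the matched analysis to PGx subjects who met an ESAS cutoff (pain ≥4 and/or depression ≥3) at the first or re-establishment visit.
2. Apply the same cutoff to every control, including screen failures, and bring section 5 into line.
3. Name first-visit ESAS pain and depression as covariates in both between-group analyses (the mixed models and the comparison of average post-baseline scores).
4. Report subjects who entered only by the diagnosis route in the single-arm analysis, with their number.

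Eligibility for the trial does not change. The cost is a few sentences, somewhat fewer PGx subjects in the matched comparison (SE up by a factor of about 1.02 to 1.12 at assumed shares of 5–20%), and a matched estimate that applies only to subjects who met an ESAS cutoff.

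Opening the control pool to diagnosed patients whose depression drug was actually changed is not a good substitute. Section 3.2 asks only for a provider-identified need, so the two cohorts would again have different entry rules.
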